### 6.4 Missing values and sensitivity analyses

#### (1)

Missing values in questionnaires (single items are missing) will be completed by applying questionnaire-specific rules. If no such rules exist, missing individual values will be replaced by the median of the other items for the respective patient from the visit concerned, unless more than 25% of items are missing. If more than 25% of the items are missing, the entire score qualifies as missing.

#### (2)

There are various reasons for assuming why patients complete the AST or SOC physiotherapy.

If less than 10% of values are missing for the primary outcome variable, complete case analysis is effective. If more values are missing, various approaches meeting the criteria of sensitivity analyses are employed that cover a worst-case and a best-case scenario.

### **6.5 *Investigation of covariates***

Additional potential variables are included in the primary covariance model as fixed factors. This applies to baseline data describing the response to treatment between enrollment and baseline visit.

A mixed model is also implemented for the primary outcome measure in which the sites are included as random effects in order to address any patient-site dependencies.

### **6.6 *Safety data***

Safety data are described on the basis of the safety population. The data are broken down by severity, intensity, required treatment, system organ class, causal relationship, treatment outcome, and action taken.

### **6.7 *Sample size planning***

Ciprian et al. (2013), Masiero et al. (2014) and Ygrit et al. (2013) have shown that populations receiving structured physiotherapy improve their BASMI score by one point versus control groups (Liang et al. 2015). A detectable difference of one BASMI point, a power of 80% and a standard deviation of 3.7 gives a calculated population size of 216 patients in the active arm (432 patients in total).

In view of the complex enrollment process, relatively long study duration, and physical activity/participation on the part of patients, we expect a dropout rate of 15%. All this gives a final sample size of 510 patients ( $216 * 2 * 1/0.85$ ) for the study.

### **6.8 *Interim analysis***

An interim analysis is not planned.

### **6.9 *Statistical software***

All analyses will be run using SAS 9.4® software (SAS Institute Inc. Cary, NY, USA) on Windows 10.

## 7 List of Tables and Lists

### 1 Demographic data and admission characteristics (Descriptive statistics)

#### 1.1 Patient characteristics

- Table 1.1.1: First patient in / Last patient out
- Table 1.1.2: Inclusion criteria
- Table 1.1.3: Exclusion criteria
- Table 1.1.4: Visits
- Table 1.1.5: Treatment groups
- Table 1.1.6: Age by treatment group
- Table 1.1.7: Sex by treatment group
- Table 1.1.8: Weight by treatment group
- Table 1.1.9: Height by treatment group
- Table 1.1.10: BMI by treatment group
- Table 1.1.11: Disease duration by treatment group
- Table 1.1.12: Family history by treatment group
- Table 1.1.13: Smoking by treatment group
- Table 1.1.14: CRP by treatment group
- Table 1.1.15: BSG by treatment group
- Table 1.1.16: HLA-B27 by treatment group
- Table 1.1.17: Disease activity by treatment group
- Table 1.1.18: Employment by treatment group
- Table 1.1.19: Joint surgery by treatment group

#### 1.2 Comorbidities

- Table 1.2.1: Comorbidities - Type by treatment group
- Table 1.2.2: Comorbidities - Medication by treatment group

#### 1.3 Prior or current axSpA-therapy

##### 1.3.1 NSAR

- Table 1.3.1.1: Prior or current NSAR by treatment group
- Table 1.3.1.2: Prior NSAR by treatment group
- Table 1.3.1.3: Current NSAR by treatment group

##### 1.3.2 Biologicals

- Table 1.3.2.1: Prior biologicals by treatment group
- Table 1.3.2.2: Current biologicals by treatment group

##### 1.3.3 Concomitant therapy

- Table 1.3.3.1: Prior concomitant therapy by treatment group
- Table 1.3.3.2: Current concomitant therapy by treatment group

#### 1.4 Type of physical therapy

- Table 1.4.1: Prior or current physical therapy by treatment group
- Table 1.4.2: Prior physical therapy
- Table 1.4.3: Current physical therapy by treatment group
- Table 1.4.4: Movement / physical activity by treatment group

#### 1.5 Pain

Table 1.5.1: Overall pain by treatment group

Table 1.5.2: Back pain by treatment group

Table 1.5.3: Pain at night by treatment group

## 2 Efficacy Data (Descriptive statistics)

### 2.1 Primary endpoint

Table 2.1.1: Improvement of spinal mobility after 6 month from Baseline Visit

### 2.2 Secondary endpoints

Table 2.2.1: Spinal mobility – Evaluated by the Bath Ankylosing Spondylitis Metrology Index [BASMI]

Table 2.2.2: Physical Function – Evaluated by the BASFI NRS score

Table 2.2.3: Overall functioning by ASAS Health Index (HI)

Table 2.2.4: Disease activity as measured by Bath AS Disease Activity Index (BASDAI)

Table 2.2.5: Percentage of patients achieving 50% improvement in BASDAI (BASDAI 50 response)

Table 2.2.6: Disease activity as measured by Ankylosing Spondylitis Disease Activity Score (ASDAS)

Table 2.2.7: Percentage of patients in ASDAS inactive disease (ASDAS < 1.3)

Table 2.2.8: Percentage of patients with low disease activity (ASDAS < 2.1)

Table 2.2.9: Percentage of subjects with moderate disease activity (ASDAS >= 1.3 to < 2.1)

Table 2.2.10: Percentage of subjects with high disease activity (ASDAS >= 2.1 to < 3.5)

Table 2.2.11: Percentage of subjects with very high disease activity (ASDAS >= 3.5)

Table 2.2.12: ASDAS major improvement (delta >= 2.0)

Table 2.2.13: ASDAS clinically important improvement (delta >= 1.0)

Table 2.2.14: ASAS20 response: Patient's Global Assessment

Table 2.2.15: ASAS20 response: Pain

Table 2.2.16: ASAS20 response: Function

Table 2.2.17: ASAS20 response: Inflammation

Table 2.2.18: ASAS40 response

Table 2.2.19: ASAS partial remission

Table 2.2.20: Change from baseline in Physician's Global Assessment of Disease Activity

Table 2.2.21: Change from baseline in Patient's Global Assessment of Disease Activity

Table 2.2.22: Patient's global assessment of pain

Table 2.2.23: Patient's assessment of total back pain

Table 2.2.24: Patient's assessment of nocturnal back pain

Table 2.2.25: Work Ability Index (modified WAI)

Table 2.2.26: Fatigue (BASDAI question 1)

Table 2.2.27: Duration and severity of morning stiffness

Table 2.2.28: Fear avoidance behavior (FABQ)

Table 2.2.29: Comorbid conditions

Table 2.2.30: Concomitant medications: Prior and concomitant non-biologic disease-modifying antirheumatic drugs (DMARDs)

Table 2.2.31: Concomitant medications: Concomitant systemic glucocorticoids

Table 2.2.32: Concomitant medications: Concomitant pain relief medications: analgesics, non-selective nonsteroidal anti-rheumatic drugs (NSAIDs), cyclooxygenase-2 (COX-2) inhibitors

**3 Safety (Descriptive statistics)**

## 3.1 (Serious) adverse events

## 3.1.1 Details of (serious) adverse events

Table 3.1.1.1: Number of (serious) adverse events

Table 3.1.1.2: Number of (serious) adverse events by visit

Table 3.1.1.3: (Serious) adverse events and intensity

Table 3.1.1.4: (Serious) adverse events and seriousness

Table 3.1.1.5: (Serious) adverse events and outcome

Table 3.1.1.6: (Serious) adverse events and actions taken

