11.1.3 Relationship to Pharmaceutical Product

The following definitions will be used to assess the relationship of the adverse event to the use of product:

Reasonable Possibility An adverse event where there is evidence to suggest a causal relationship between the product and the adverse event.

No Reasonable Possibility An adverse event where there is no evidence to suggest a causal relationship between the product and the adverse event.

If no reasonable possibility of being related to product is given, an alternate etiology must be provided for the adverse event.

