## 6 Statistical methods

### 6.1 Analysis populations

Safety population: all patients enrolled into the study who received at least one dose of Humira® (adalimumab)

ITT population: all randomized patients

Per-protocol (PP) population: all randomized patients who underwent AST or SOC physiotherapy for 6 months with no major protocol deviations.

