## 3.1.2 Details of (serious) adverse events by SOC and PT

Table 3.1.2.1: Intensity by SOC and PT

Table 3.1.2.2: Seriousness by SOC and PT

Table 3.1.2.3: Outcome by SOC and PT

Table 3.1.2.4: Actions taken by SOC and PT

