**4 Further tables (Descriptive statistics)**

## 4.1 Disease activity

Table 4.1.1: Disease activity by visit and treatment group

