## 4.3 Type of physical therapy

Table 4.3.1: Physical therapy by visit and treatment group

Table 4.3.2: Details on physical therapy by visit and treatment group

Table 4.3.3: Movement / physical activity by visit and treatment group

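### No safety passage or table title provides for adverse events by randomised arm, so the planned summaries do not compare training with standard-of-care physiotherapy

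*SAP*

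**What the plan says.** **Safety set.** SAP 6.1 defines it as "Safety population: all patients enrolled into the study who received at least one dose of Humira® (adalimumab"); Protocol 9.7.1 agrees. Randomisation is not required. The randomised set is defined beside it ("ITT population: all randomized patients") and is the basis of the primary efficacy analysis, but it is not named for safety.

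**Collection period.** Under Protocol 11.1.4, reporting starts at consent. The visit schedules record AEs from V0, when adalimumab starts. Allocation takes effect at V3, after an enrolment period of 3 to 5 months (SAP 4.3).

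**Breakdowns.** SAP 6.6 says: "The data are broken down by severity, intensity, required treatment, system organ class, causal relationship, treatment outcome, and action taken". SAP 4.8 and Protocol 9.7.7 give the same list. Arm is not in it.

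**Tables.** In SAP 7, block 3, the AE tables are untitled as to group, by visit ("Table 3.1.1.2: Number of (serious) adverse events by visit") or by coding level ("Table 3.1.2.1: Intensity by SOC and PT"). The laboratory and pregnancy tables are by visit. Block 4 is worded differently: "Table 4.1.1: Disease activity by visit and treatment group" and "Table 4.3.1: Physical therapy by visit and treatment group" are typical.

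**Causality.** Protocol 11.1.3 rates relationship to the drug only. Where no reasonable possibility of a drug relationship is given, "an alternate etiology must be provided for the adverse event".

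**The concern.** Both arms receive adalimumab. What is randomised is supervised machine-based training (Protocol Annex 1) against physiotherapy at the therapist's discretion. The comparison that randomisation makes interpretable for safety is therefore AEs after allocation, arm against arm. The safety plan is built around the drug instead: its denominator, its collection window and its causality scale all refer to adalimumab.

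The protocol hypothesises that training is superior (Protocol 8.0) and gives patients' physical exposure as one reason to expect dropout (Protocol 9.5). The safety record it cites for the training comes from back-pain patients (Annex 1). If the plan is followed as written, a benefit of training could be reported with no summary of its harms against the comparator, although Protocol 11.1.5 requires serious and non-serious AEs to be actively solicited.

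**Working it through.** The point concerns no figure stated in the plan. The check is a reading of the passages, followed by simple arithmetic.

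**1. Do the titles name arm?**

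| SAP 7 block | Titles naming treatment group | Arm comparison specified in the text? |
|---|---|---|
| 1 Demographics and admission | nearly all (not 1.1.1 to 1.1.4 or 1.4.2) | descriptive only |
| 2 Efficacy | none | yes, SAP 6.3 |
| 3 Safety | 0 of 13 (6 + 4 + 3) | no |
| 4 Further tables | 87 of 87 | the titles state it |

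Block 2 shows that a missing label does not by itself mean a pooled table. What sets block 3 apart is that neither title nor text supplies the arm. CRP and BSG show the contrast: by treatment group in Tables 1.1.14 and 1.1.15, by visit only in 3.2.1 and 3.2.2.

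In the titles by SOC and PT, SOC has to be read as system organ class, the breakdown named in SAP 6.6. The SAP abbreviation list defines SOC only as standard of care, but these titles do not denote the comparator arm.

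**2. Are the promised breakdowns tabulated?** Intensity, outcome, action taken and system organ class have tables. Causal relationship and required treatment have none.

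**3. How much observation precedes allocation?** Inputs: run-in of 3 to 5 months and follow-up of 12 months (SAP 4.3). The share for a completer is m/(m + 12): 3/15 = 20% and 5/17 = 29%.

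**4. How many patients in the safety set might have no arm?** Input: 510 enrolled (Protocol 9.2 and 9.5, SAP 4.6). The documents give no rate of failure at V1 or V2, so 10% to 40% is an assumption. 510 × 0.10 = 51 and 510 × 0.40 = 204, leaving 459 to 306 randomised.

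**5. What does pooling hide?** AE rates are not given, so both examples are illustrations that assume all 510 are randomised 1:1 (255 per arm).

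- *Rates.* Suppose training doubles the AE rate after V3 and all patients complete. The pooled rate rises by (m + 6 × 2 + 6)/(m + 12): 21/15 = 1.40 for m = 3 and 23/17 = 1.35 for m = 5. Restricted to follow-up visits it is (6 × 2 + 6)/12 = 1.5. In neither case can the rise be attributed to an arm.
- *Counts.* A pooled 76/510 = 14.9% fits each of these splits (difference p1 − p2, 95% CI ± 1.96 × √[p1(1−p1)/255 + p2(1−p2)/255]):

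| Training v SOC | Difference (points) | 95% CI |
|---|---|---|
| 38 v 38 | 0 | −6.2 to +6.2 |
| 51 v 25 | +10.2 | +4.1 to +16.3 |
| 60 v 16 | +17.3 | +11.3 to +23.3 |

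A pooled summary cannot tell these apart.

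**The case against.** The strongest reply is that this infers absence from table titles. No block 2 title carries the arm, not even primary Table 2.1.1, yet efficacy will plainly be compared by arm; the programmers may well add arm columns to the AE tables too. That stands as a limit: the documents do not say that AEs will be pooled. They give no instruction to split them, and no safety text plays the part that SAP 6.3 plays for efficacy.

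Other replies stand in part.

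- Table 3.1.1.2 is by visit, and patients who fail at V1 or V2 do not go on to V4 to V7. It can therefore largely separate run-in events and never-randomised patients from follow-up, but as titled it stays pooled over arms.
- Listing 5.9 gives patient-level AEs. If it carries arm, counts can be rebuilt; its columns are not stated. A reader might infer that harm from training cannot be seen at all. The documents do not support that: the gap is in the planned summaries, not shown to be in the data. Flares would also show in part in block 4, in disease activity, BASDAI, ASDAS, pain and NSAID use by arm.
- The all-enrolled safety set might be taken for an error. It is not: it matches the drug-reporting duty that starts at consent. It is only not enough for the randomised question.
- The study is exploratory, and Protocol 11.1.5 says it is not designed to identify or quantify a hazard of the drug. That does not speak to the training, and descriptive counts by arm need no test.

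**Conclusion.** The point holds as a gap in the planned summaries. The safety text lists seven breakdowns without arm, none of the 13 safety titles supplies it, and causality is rated only against the drug common to both arms. Following the plan gives no AE comparison between training and standard-of-care physiotherapy, the only randomised factor.

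The run-in share of 20% to 29% is firm for completers. The 51 to 204 patients without an arm rests on an assumed 10% to 40% not randomised. A reader might instead take 510 as the number randomised and work back to a larger enrolment. The documents do not support that: they give 510 as the number enrolled and nowhere state that 510 will be randomised. The count and rate examples show only what pooling would conceal; they are not predictions.

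The missing causality and required-treatment tables are a separate, smaller mismatch between SAP 6.6 and SAP 7, and stand whatever is decided about arm. The SAP should be amended; sample size and primary analysis are unaffected.

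**What to change.** 1. State in SAP 6.1 and 6.6 that AEs in randomised patients occurring after V3 are summarised descriptively by randomised arm. Assign events by onset date if the eCRF captures it, otherwise by reporting visit (V4 to V7). Neither document says that onset date is collected, so the rule should cover both cases.
2. Produce Tables 3.1.1.x and 3.1.2.x on that basis, with number and percentage of patients, number of events and follow-up time per arm.
3. Keep the all-enrolled drug-safety tables from V0 as a separate block.
4. Add the causality and required-treatment tables that SAP 6.6 already promises.
5. Define the second meaning of SOC in the abbreviation list.
6. Optionally, code the alternate etiology for training or physiotherapy and show it by arm. This depends on the field existing in the eCRF. It is required only where no reasonable possibility of a drug relationship is given, and attribution by staff who know the allocation would be subjective, so it should not replace the counts by arm.

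The cost of items 1 to 5 is SAP wording and table programming.

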## 3.1.2 Details of (serious) adverse events by SOC and PT

Table 3.1.2.1: Intensity by SOC and PT

Table 3.1.2.2: Seriousness by SOC and PT

Table 3.1.2.3: Outcome by SOC and PT

Table 3.1.2.4: Actions taken by SOC and PT

## 3.2 Laboratory

Table 3.2.1: CRP by visit

Table 3.2.2: BSG by visit

Table 3.2.3: Pregnancy by visit

**4 Further tables (Descriptive statistics)**

## 4.1 Disease activity

Table 4.1.1: Disease activity by visit and treatment group

## 4.2 axSpA-therapy

Table 4.2.1: NSAR by visit and treatment group

Table 4.2.2: Details on NSAR by visit and treatment group

Table 4.2.3: Details on biologicals by visit and treatment group

Table 4.2.4: Details on concomitant therapy by visit and treatment group

## 4.3 Type of physical therapy

Table 4.3.1: Physical therapy by visit and treatment group

Table 4.3.2: Details on physical therapy by visit and treatment group

Table 4.3.3: Movement / physical activity by visit and treatment group

## 4.4 Bath Ankylosing Spondylitis Metrology Index (BASMI)

Table 4.4.1: BASMI item 1 by visit and treatment group

Table 4.4.2: BASMI item 2 by visit and treatment group

Table 4.4.3: BASMI item 3 by visit and treatment group

Table 4.4.4: BASMI item 4 by visit and treatment group

Table 4.4.5: BASMI item 5 by visit and treatment group

Table 4.4.6: BASMI total score by visit and treatment group

## 4.5 Bath Ankylosing Spondylitis Functional Index (BASFI)

Table 4.5.1: BASFI item 1 by visit and treatment group

Table 4.5.2: BASFI item 2 by visit and treatment group

Table 4.5.3: BASFI item 3 by visit and treatment group

Table 4.5.4: BASFI item 4 by visit and treatment group

Table 4.5.5: BASFI item 5 by visit and treatment group

Table 4.5.6: BASFI item 6 by visit and treatment group

Table 4.5.7: BASFI item 7 by visit and treatment group

Table 4.5.8: BASFI item 8 by visit and treatment group

Table 4.5.9: BASFI item 9 by visit and treatment group

Table 4.5.10: BASFI item 10 by visit and treatment group

Table 4.5.11: BASFI total score by visit and treatment group

#### 4.6 Assessment of SpondyloArthritis international Society (ASAS)

Table 4.6.1: ASAS item 1 by visit and treatment group

Table 4.6.2: ASAS item 2 by visit and treatment group

Table 4.6.3: ASAS item 3 by visit and treatment group

Table 4.6.4: ASAS item 4 by visit and treatment group

Table 4.6.5: ASAS item 5 by visit and treatment group

Table 4.6.6: ASAS item 6 by visit and treatment group

Table 4.6.7: ASAS item 7 by visit and treatment group

Table 4.6.8: ASAS item 8 by visit and treatment group

Table 4.6.9: ASAS item 9 by visit and treatment group

Table 4.6.10: ASAS item 10 by visit and treatment group

Table 4.6.11: ASAS item 11 by visit and treatment group

Table 4.6.12: ASAS item 12 by visit and treatment group

Table 4.6.13: ASAS item 13 by visit and treatment group

Table 4.6.14: ASAS item 14 by visit and treatment group

Table 4.6.15: ASAS item 15 by visit and treatment group

Table 4.6.16: ASAS item 16 by visit and treatment group

Table 4.6.17: ASAS item 17 by visit and treatment group

Table 4.6.18: ASAS total score by visit and treatment group

#### 4.7 Bath Ankylosing Spondylitis Disease Activity Index (BASDAI)

Table 4.7.1: BASDAI item 1 by visit and treatment group

Table 4.7.2: BASDAI item 2 by visit and treatment group

Table 4.7.3: BASDAI item 3 by visit and treatment group

Table 4.7.4: BASDAI item 4 by visit and treatment group

Table 4.7.5: BASDAI item 5 by visit and treatment group

Table 4.7.6: BASDAI item 6 by visit and treatment group

Table 4.7.7: BASDAI total score by visit and treatment group

#### 4.8 Work Ability Index (WAI)

Table 4.8.1: WAI item 1 by visit and treatment group

Table 4.8.2: WAI item 2 by visit and treatment group

Table 4.8.3: WAI item 3a by visit and treatment group

Table 4.8.4: WAI item 3b by visit and treatment group

Table 4.8.5: WAI item 4a by visit and treatment group

Table 4.8.6: WAI item 4b by visit and treatment group

Table 4.8.7: WAI item 4c by visit and treatment group

Table 4.8.8: WAI item 4d by visit and treatment group  
Table 4.8.9: WAI item 4e by visit and treatment group  
Table 4.8.10: WAI item 4f by visit and treatment group  
Table 4.8.11: WAI item 5 by visit and treatment group  
Table 4.8.12: WAI item 6a by visit and treatment group  
Table 4.8.13: WAI item 6b by visit and treatment group  
Table 4.8.14: WAI item 6c by visit and treatment group  
Table 4.8.15: WAI total score by visit and treatment group  
4.9 Fear Avoidance Belief Questionnaire (FABQ)  
Table 4.9.1: FABQ item 1 by visit and treatment group  
Table 4.9.2: FABQ item 2 by visit and treatment group  
Table 4.9.3: FABQ item 3 by visit and treatment group  
Table 4.9.4: FABQ item 4 by visit and treatment group  
Table 4.9.5: FABQ item 5 by visit and treatment group  
Table 4.9.6: FABQ item 6 by visit and treatment group  
Table 4.9.7: FABQ item 7 by visit and treatment group  
Table 4.9.8: FABQ item 8 by visit and treatment group  
Table 4.9.9: FABQ item 9 by visit and treatment group  
Table 4.9.10: FABQ item 10 by visit and treatment group  
Table 4.9.11: FABQ item 11 by visit and treatment group  
Table 4.9.12: FABQ item 12 by visit and treatment group  
Table 4.9.13: FABQ item 13 by visit and treatment group  
Table 4.9.14: FABQ item 14 by visit and treatment group  
Table 4.9.15: FABQ item 15 by visit and treatment group  
Table 4.9.16: FABQ item 16 by visit and treatment group  
Table 4.9.17: Score FABQ-PA by visit and treatment group  
Table 4.9.18: Score FABQ-W by visit and treatment group  
4.10 Ankylosing Spondylitis Disease Activity Score (ASDAS)  
Table 4.10.1: ASDAS total score by visit and treatment group  
4.11 Pain  
Table 4.11.1: Overall pain by visit and treatment group  
Table 4.11.2: Back pain by visit and treatment group  
Table 4.11.3: Pain at night by visit and treatment group

## 5 Listings

Listing 5.1: In- and exclusion criteria  
Listing 5.2: Demographic data and baseline characteristics  
Listing 5.3: Joint replacement surgery  
Listing 5.4: Comorbidities  
Listing 5.5: Laboratory  
Listing 5.6: Disease activity and pain  
Listing 5.7: axSpA-therapy  
Listing 5.8: Physical therapy

Listing 5.9: Adverse Events

Listing 5.10: Bath Ankylosing Spondylitis Metrology Index (BASMI)

Listing 5.11: Bath Ankylosing Spondylitis Functional Index (BASFI)

Listing 5.12: Assessment of SpondyloArthritis international Society (ASAS)

Listing 5.13: Bath Ankylosing Spondylitis Disease Activity Index (BASDAI)

Listing 5.14: Work Ability Index (WAI)

Listing 5.15: Fear Avoidance Belief Questionnaire (FABQ)

Listing 5.16: Ankylosing Spondylitis Disease Activity Score (ASDAS)
